### 3.3 Target sample size

The sample includes 164 cases, with 41 cases each for the placebo group, low-dose group (0.5 g/administration/day), intermediate-dose group (1.0 g/administration/day), and high-dose group (1.5 g/administration/dose). Each group will have 10 cases with HSIL/CIN2 at the time of registration. See Section 5.2 of the trial protocol for the setting basis.

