### 6. Statistical analysis policy

### 6.1 Significance level and confidence level

Unless otherwise specified, tests are two-sided tests with a significance level of 0.05, and the confidence interval is a two-sided confidence interval with a confidence coefficient of 95%.

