### 6.2 Multiplicity adjustment

Given that this trial is a phase I/II trial, multiplicity was not considered in either pairwise comparisons or dose-response evaluations using the maximum contrast method of the response rate, which is the primary efficacy endpoint, between each dose group and the placebo group. Additionally, multiplicity of tests will not be considered when tests are repeated for secondary endpoints.

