#### 7.3.3. Exploratory analysis

1) Investigation of the distribution of the E7 protein expression level (absolute quantification value) before first administration

Target FAS

population:

Analysis Calculate summary statistics (number of cases, mean, standard deviation, content: minimum, median, maximum, first quartile, third quartile) of the E7 protein expression level (absolute quantification value) and display them in a box plot for each diagnosis (CIN2, CIN3) and the overall diagnosis.

2) Investigation of the relationship between the E7 protein expression level (absolute quantification value) before first administration and the improvement effect of IGMKK16E7

Target FAS

population:

Analysis Explore whether the E7 protein expression level (absolute quantification value)

content: before the first dose can be a predictor of the therapeutic effect of IGMKK16E7. Here, a predictor of the therapeutic effect is a factor for which a higher therapeutic effect of IGMKK16E7 can be expected according to its value. The regression rate at weeks 16, which is the primary endpoint, is used as the therapeutic effect. The specific analysis procedure is described below.

1. Cases when the E7 protein expression level before first administration are divided into two categories (see definition section):

1-1) The following analysis is conducted for each of the three cases related to the presence or absence of IGMKK16E7 administration (see definition section). 1-2) Set a value, C, for all possible classifications of E7 protein expression level before first administration. For each C, the number of cases and the response rate are calculated for the presence or absence of IGMKK16E7 administration for each of the categories "less than C" and "C or greater." However, when the number of cases for either "administration present" or "administration absent" is less than two, the analysis using the applicable classification value C will not be conducted.

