1-3) For each C, conduct a logistic regression analysis where the presence or absence of response is set as the response variable; and the presence or absence of IGMKK16E7 administration, E7 protein expression level before first administration, and interaction between the presence or absence of IGMKK16E7 administration and E7 protein expression level before first administration (henceforth, referred to as "interaction") are set as the explanatory variables. Then, record the p-value of the interaction. Additionally, create a plot of the p-value of the interaction for each case.

1-4) Referencing the p-value plot of the above-mentioned interaction, output the analysis result under each of the classification values among all the possible classification C values where the p-value of the interaction is at a minimum (or 2–3 that are close to the minimum). Specifically, output the estimated value of the regression coefficient of the logistic regression as well as the odds ratio of the IGMKK16E7 response with respect to that of the placebo for each category of "less than C" and "C or greater" of the E7 protein expression level before the first administration. Additionally, create a plot of the estimated value of the response rates for each of the IGMKK16E7 and placebo for each category of "less than C" and "C or greater" of the E7 protein expression level before the first administration, and their two-sided 95% confidence interval. Use the Clopper–Pearson method to calculate the 95% confidence interval.

2. Cases where the E7 protein expression level before first administration is classified into three categories:

2-1) Conduct the following analyses in each of the three cases related to the presence or absence of IGMKK16E7 administration.

2-2) Set all possible classification value pairs C1 and C2 (>C1) of the E7 protein expression level before first administration. For each pair of C1 and C2, calculate the number of cases and the response rate of the presence or absence of IGMKK16E7 administration for each category of "less than C1," "C1 or greater and less than C2," and "C2 or greater." However, when the number of cases for either "administration present" or "administration absent" is less than two, the analysis using the applicable classification value pair C1 and C2 will not be conducted.

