C (or C1 and C2) is the scaled classification value of the E7 protein expression level. Order statistics of the E7 protein expression level are used to set all possible values of the classification value C (or C1 and C2) in a sequential manner. At that time, classification values in either of the two categories of "less than C" or "C or higher" (or three categories of "less than C1," "C1 or higher and less than C2," or "C2 or higher"), where the number of cases for either category of "administration present" or "administration absence" of the IGMKK16E7 administration below is less than two, are excluded from the investigation.

• Presence or absence of IGMKK16E7 administration. The following three cases are investigated.

Case	IGMKK16E7 administration		Content
	Administration	Administratio	
	present	n absent	
1	High-dose group	Placebo	IGMKK16E7 vs. placebo
	+	group	
	intermediate-dos		
	e group +		
	low-dose group		
2	High-dose group	Placebo	High and intermediate dose
	+	group	of IGMKK16E7 vs.
	intermediate-dos		placebo
	e group		
3	High-dose group	Placebo	High dose of IGMKK16E7
		group	vs. placebo

3) Investigation of the relationship between changes in the E7 protein expression level (relative quantification value) after administration and pathological judgment

Target FAS

population:

Analysis For each of the three IGMKK16E7 dose groups of the IGMKK16E7 content: administration group (high-dose group + intermediate-dose group + low-dose group) and the placebo group, summary statistics are calculated for the magnitude and rate of change in the E7 protein expression level (relative quantification value) after administration for each category of the pathological judgment results after administration.

> • Categories of pathological judgment results: "CR," "PR," "SD," "PD," "NE," "response (CR or PR)," and "non-response (SD or PD)"

• Evaluation time points: 16 and 24 weeks after the first dose

4) Investigation of the relationship between the presence or absence of an HPV E7-specific immune response before first administration and the improvement effect of IGMKK16E7

Target FAS

population:

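### The exploratory E7 cut-point search reports effect estimates at the smallest interaction p-value with no correction for the search, so chance alone can yield a small p-value and inflated odds ratios

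*SAP*

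**What the plan says.** Item 2) of Section 7.3.3 asks whether baseline E7 (absolute quantification) "before the first dose can be a predictor of the therapeutic effect of IGMKK16E7". The outcome is week-16 response, the primary endpoint.

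- **Two categories.** Step 1-2: "Set a value, C, for all possible classifications of E7 protein expression level before first administration". Step 1-3 fits a logistic model with treatment, E7 category and their interaction at each C, records the interaction p-value and plots it.
- **Three categories.** Step 2-2: "Set all possible classification value pairs C1 and C2 (>C1) of the E7 protein expression level before first administration". Step 2-3 does the same with E7 as a three-level ordinal score.
- **Restriction.** Cuts for which a treatment-by-category count "is less than two, are excluded from the investigation".
- **Selection and output.** Steps 1-4 and 2-4 report results at the cut or pair "where the p-value of the interaction is at a minimum (or 2–3 that are close to the minimum". Both output regression coefficients, and response rates with Clopper-Pearson 95% intervals. The two-category search also outputs the odds ratio against placebo in each E7 category.
- **Groupings.** All doses, high plus intermediate, and high alone, each against placebo. With two categorisations this makes six searches.

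Section 6.1 sets the default: "Unless otherwise specified, tests are two-sided tests with a significance level of 0.05". Section 6.2 waives adjustment for the primary endpoint and says "multiplicity of tests will not be considered when tests are repeated for secondary endpoints". It does not mention exploratory tests. Section 4.1.2 separately fixes median and tertile categories of baseline E7 as a stratification factor.

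**The concern.** The smallest of many correlated p-values is not distributed like a single p-value, and an estimate taken where the contrast looks most extreme is biased away from no effect. The SAP plans no permutation reference, shrinkage, validation or caveat. A colleague reading the selected cut against the 0.05 default of Section 6.1 could take an ordinary chance result for evidence that E7 predicts benefit, with odds ratios several times too large beside it. What is at stake is whether this exploratory question gets an interpretable answer.

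**Working it through.** **Plan's own figure.** The SAP states no error rate or expected effect for this search, so there is nothing to reproduce. The only design arithmetic holds: 4 x 41 = 164.

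**Inputs from the SAP**
- Section 3.3: "The sample includes 164 cases, with 41 cases each for the placebo group, low-dose group". The groupings are therefore 123 v 41 (164 patients), 82 v 41 (123) and 41 v 41 (82).
- Section 7.3.3: at least two patients per treatment-by-category cell.
- Section 6.1: two-sided 0.05.

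**Assumptions**
- Response rates: Section 3.3 defers the sample-size basis to the protocol, so rates of 10-50% were tried, either equal in all arms or higher on drug.
- E7 is unrelated to response and to the drug effect, with no ties and no missing data.
- The SAP does not say whether the interaction p-value is Wald or likelihood-ratio. Wald is used unless stated. Cuts with infinite estimates are given p = 1.

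**Size of the search**

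| Patients | Cuts before exclusion | Admissible cuts | Pairs before exclusion | Admissible pairs |
|---|---|---|---|---|
| 164 | 163 | about 149 | 163 x 162 / 2 = 13,203 | about 10,000 |
| 123 | 122 | about 111 | 122 x 121 / 2 = 7,381 | about 5,550 |
| 82 | 81 | about 72 | 81 x 80 / 2 = 3,240 | about 2,280 |

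**Test at one cut.** With x responders among n patients in each of the four cells, let L = log[x/(n - x)]. Then:

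- d = (L active,high - L placebo,high) - (L active,low - L placebo,low)
- SE(d) = square root of the sum over the four cells of [1/x + 1/(n - x)]
- p = 2[1 - Φ(|d|/SE)]
- ratio of odds ratios = exp(|d|), whose true value here is 1

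The search keeps the cut with the smallest p.

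**Share of trials (%) with minimum p < 0.05, marker with no predictive value** (600 simulated trials per row; Monte Carlo standard error at most √(0.25/600) = 2 points). Triplets are all doses, high plus intermediate, high alone.

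| Response, active / placebo | One two-category search | Any of three two-category | One three-category search | Any of six |
|---|---|---|---|---|
| 10 / 10 | 15.0, 10.3, 3.5 | 18.7 | 38.2, 39.3, 29.2 | 52.3 |
| 20 / 20 | 27.3, 24.8, 19.3 | 37.5 | 48.7, 48.2, 43.2 | 67.5 |
| 30 / 30 | 34.0, 31.3, 28.0 | 45.0 | 52.8, 52.0, 49.5 | 70.8 |
| 40 / 40 | 34.3, 35.2, 29.2 | 51.0 | 52.5, 55.3, 49.5 | 73.8 |
| 40 / 20 | 28.8, 29.0, 26.8 | 41.8 | 45.2, 47.0, 45.7 | 63.8 |

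Further results for one two-category search:
- A separate run of 4,000 trials per setting at 30/15, 25/25 and 35/20 (active/placebo) gave 26-30%, 24-28% and 20-24% for the three groupings.
- At 50% response in all arms (1,000 trials): 34.8%, 35.8% and 29.1%. The range over 10-50% response is thus about 3-36%.
- A fixed median split gives 0-6%. Likelihood-ratio p-values give 44-63% for the minimum.

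**Estimates at the selected two-category cut.** The median ratio of odds ratios, in either direction, is about 7-8 at 15-35% response and about 6-8 over the wider set of rates. Among trials with minimum p < 0.05 it is about 9-30.

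**Planned intervals.** At 15-35% response, the Clopper-Pearson intervals for response rates at the selected cut cover about 93-95% overall and about 86-89% when the minimum p is below 0.05.

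**Minimum cell size.** At 30% response, raising it from 2 to 8 lowers the triplet from 34.0, 31.3, 28.0 to 30.8, 28.3, 25.8.

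**The case against.** The strongest reply is that the SAP calls this analysis exploratory, plots the interaction p-values over the search, shows two or three near-minimum cuts as well as the minimum, and sets no rule by which E7 is declared predictive. All of that is correct, and it lowers the severity. It does not answer the point: the plot discloses that a search took place, but not how small a minimum p chance alone produces, and it leaves the odds ratios at the selected cut uncorrected.

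Four stronger readings are tempting, and the document does not support them:

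- **That the reported intervals are far too narrow.** The only intervals planned here are Clopper-Pearson intervals for response rates; none is specified for the odds ratio or the interaction. The planned ones are only mildly affected.
- **That the result will steer patient selection in a later trial.** Section 2 gives the purpose as safety and the recommended dose. No action is tied to the E7 result.
- **That every grouping searches 13,203 pairs.** That is the count for 164 patients before the two-per-cell exclusion.
- **That cells with no responders, or only responders, drive the selection.** A cut with infinite estimates has a Wald p near 1 and would not be chosen. In the three-category model, the ordinal score means one such cell does not by itself make the interaction inestimable.

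**Conclusion.** The point holds, as a minor one. Section 7.3.3 item 2) selects on the minimum interaction p-value and reports coefficients, and for two categories odds ratios, as though the cut had been fixed in advance. A reader might take 20-30% as a fixed property of this trial. It is not: it applies to one two-category Wald search at an assumed 15-35% response. The rate is lower when response is rare and higher with likelihood-ratio tests, with three categories or over all six searches. The inflation of the ratio of odds ratios is the steadier result, staying at about 6-8 over the rates tried. All figures assume 41 evaluable patients per arm, no ties and no marker effect. That E7 looks predictive below 0.05 is an inference from the Section 6.1 default, not a decision rule in the SAP. The primary analysis is unaffected.

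**What to change.** Keep the search and add to Section 7.3.3 item 2):

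1. A permutation or parametric-bootstrap p-value for the minimum, repeating the whole search in each replicate, ideally across all six searches. State whether the interaction test is Wald or likelihood-ratio.
2. Bootstrap-corrected odds ratios at the selected two-category cut, beside the uncorrected ones.
3. The interaction test at the median and tertile categories of Section 4.1.2, or with E7 continuous, shown alongside.
4. A statement that the searched cut is hypothesis-generating.

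A larger minimum cell size is optional: it does little for the false-signal rate. The cost is SAP wording and some computing time, with no new data. The results will look less striking.

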### 7.4 Safety analysis

7.4.1.	Adverse	events /	' side	effects
--------	---------	----------	--------	---------

Item name	Definition
Adverse event	This refers to any unfavorable event occurring between the use
	(administration) and the end of use (administration) of this trial drug,
	regardless of whether or not it is related to the trial drug. During the
	follow-up period, information will be collected only for events for which a
	causal relationship cannot be rejected.
Side effect	The relationship between an adverse event and the trial drug is judged as
	"relationship cannot be denied" or "no relationship with the trial drug."
	Adverse events that fall under the former category of "relationship cannot
	be denied" are treated as a side effect.

### 7.4.1.1. Occurrence of adverse events and side effects

Target Safety analysis set

population:

Analysis
 For both the adverse events and side effects in each group, calculate the number of incident cases, number of occurrences, percentage of the number of cases (%), and their two-sided 95% confidence intervals for all events that

occurred, serious events, severe events (NCI-CTCAE Grade 3 or higher), and events that led to discontinuation of the trial drug. The denominator of the percentage (%) of the number of cases is the number of cases in the target population, and the Clopper–Pearson method is used to calculate the two-sided 95% confidence interval.

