- When the protocol was revised to Ver. 2, the permitted range for subject visits was changed; however, this change was not reflected in the analysis plan. Therefore, the range of data adoption for the evaluation periods (Section 6.4.4) was changed to reflect the permitted range of visits in the protocol.
- When the protocol was revised to Ver. 5 of this protocol, we clarified the regulations regarding histology at week 24 for cases judged to be normal at week 16. Separately, we stipulated that follow-ups up to 24 weeks would be conducted according to the diagnosis by the attending physician at the facility 16 weeks after the first dose, except for cases judged to be CIN3 requiring treatment or invasive cancer. However, this content was not reflected in this analysis plan. Therefore, the above items were added to the primary endpoint (Section 4.1.1), and the handling of missing values (Section 6.5) was revised to reflect this content.

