e: If the laboratory test was conducted on the date of consent and the administration start date was within 10 days from the date when the applicable test was conducted, there is no need to conduct a new test on the administration start date.

f: Perform at initial visit or on the administration start date. Confirm that the subject does not have HIV prior to prescribing the trial drug. Start administration of the trial drug within 14 days from the date when the applicable test was conducted.

g: Perform HPV genotyping on the same day using the collected specimen.

h: Subject shall record subjective symptoms in a health journal.

i: Confirm entries in the health journal during the administration period. The follow-up period (from week 17) shall only confirm adverse events that were clearly caused by the trial drug.

j: For subjects judged to be normal at week 16, perform only if a precancerous cervical disease was confirmed by colposcopy conducted on the same day (week 24).

k: In case retest is necessary because of the condition of the specimen, retest is permitted within 14 days from the date when the initial test was performed.

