### 4.2 Safety endpoints

1) Incidence of adverse events and side effects

This refers to any unfavorable event occurring between the use (administration) and the end of use (administration) of this trial drug, regardless of whether or not it is related to the trial drug. During the follow-up period, information will be collected only for events for which a causal relationship cannot be rejected.

2) Laboratory test values

Hematology tests, blood biochemistry tests, and urinalysis.

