### 6.7 Handling of safety data

### 6.7.1 Adverse events / side effects

Adverse events and side effects that occur after the first administration of the trial drug are targeted.

- Number of incident cases: if multiple adverse events (side effects listed in Table in the Appendix) that correspond to the same PT code (or SOC code) occur in the same subject, they will be counted as a single case.
- Incidence proportion: calculated as the number of incident cases / number of observed cases.
- Number of occurrences: if multiple adverse events (side effects listed in Table in the Appendix) that correspond to the same PT code (or SOC code) occur in the same subject, they will be counted as a single occurrence.

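### Adverse event tables pool follow-up with the earlier period, although follow-up collects only related events and who stays in it depends on the week-16 diagnosis

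*SAP*

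**What the plan says.** **Events counted.** SAP 6.7.1: "Adverse events and side effects that occur after the first administration of the trial drug are targeted". No end day is given, and none of the tables in 7.4.1.1 to 7.4.1.6 is divided by period.

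**Collection rule.** SAP 4.2 defines an adverse event as "any unfavorable event occurring between the use (administration) and the end of use (administration) of this trial drug", whether or not it is related. It then adds: "During the follow-up period, information will be collected only for events for which a causal relationship cannot be rejected". Section 7.4.1 repeats both statements. Footnote i to Table 1 is stricter: "The follow-up period (from week 17) shall only confirm adverse events that were clearly caused by the trial drug".

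**Denominator.** Section 7.4.1.1 states: "The denominator of the percentage (%) of the number of cases is the number of cases in the target population". Section 7.4.1.2 uses the same denominator. Section 6.7.1 has a different general rule, "calculated as the number of incident cases / number of observed cases", and does not define observed cases. Sections 7.4.1.3 to 7.4.1.6 name no denominator.

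**Who is followed after week 16.** Section 1.2 says follow-up to week 24 goes by the attending physician's week-16 diagnosis, "except for cases judged to be CIN3 requiring treatment or invasive cancer". Section 3.1 sends women diagnosed clinically with CIN3 or more at week 16 to standard therapy. The sentence before that, however, has every woman whose lesion is no worse than CIN3 evaluated again at week 24.

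**The concern.** There are two separate problems.

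1. **Mixed collection in the adverse event rows.** Early in the trial an event counts whatever its cause; in follow-up it is recorded only if judged related. A pooled row for all events is then an all-cause count neither to week 16 nor to week 24.
2. **Unequal observation in the adverse event and side-effect rows.** A woman who leaves at week 16 stays in the denominator but can contribute no follow-up event. Whether she leaves depends on her week-16 diagnosis, which is closely tied to the primary endpoint. Observation time can therefore differ between arms because of treatment, and randomization does not balance it.

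Section 2 gives confirming safety and determining the recommended dose as the purpose of the trial, so these percentages will be read side by side across arms. An arm with fewer women at CIN3 or cancer could show more events at the same true risk.

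**Working it through.** The SAP states no figure to reproduce here. The check is of direction and size.

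**Inputs from the SAP**
- 41 women per arm, 10 of them with CIN2 at registration (3.3), so 41 − 10 = 31 with CIN3.
- Trial period 16 weeks, follow-up 8 weeks, last planned dosing day Day 54 (3.1).
- Week 17 starts on Day 113 (6.4.4, Table 2), which is 113 − 54 = 59 days after the last planned dose.

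**Assumptions (not in the SAP)**
- a: share with an event by week 16, equal in both arms.
- q: chance of a first related event in follow-up among women still observed, equal in both arms.
- r: share of the arm kept in follow-up.

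**Formulas**
- Mean weeks observed = 16 + 8r
- Percentage shown = a + (1 − a) × q × r
- False gap between arms = (1 − a) × q × (r₁ − r₀)

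**Observation time** with r₀ = 0.45 and r₁ = 0.75: 16 + 8 × 0.45 = 19.6 weeks against 16 + 8 × 0.75 = 22.0 weeks.

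**False gap** with a = 0.10 and the same retention, i.e. 0.90 × q × 0.30:

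| q | 45% kept | 75% kept | Gap (points) | Women of 41 |
|---|---|---|---|---|
| 2% | 10.81% | 11.35% | 0.54 | 0.2 |
| 5% | 12.03% | 13.38% | 1.35 | 0.6 |
| 10% | 14.05% | 16.75% | 2.70 | 1.1 |
| 20% | 18.10% | 23.50% | 5.40 | 2.2 |

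The last row assumes twice the related-event risk in eight off-drug weeks that is assumed for the 16 weeks containing all dosing. It marks the edge of the range and is not a plausible case.

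**Sensitivity to who stays** (a = 0.10, q = 5%)
- Nearly everyone stays, 90% v 95%: 0.90 × 0.05 × 0.05 = 0.2 points.
- Extreme split, only the 10 CIN2 women stay in one arm (24%) and all 41 in the other: 0.90 × 0.05 × 0.76 = 3.4 points, or 1.4 women.

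**Scale.** The planned Clopper–Pearson interval for 4 of 41 runs from 2.7% to 23.1%, far wider than any gap at q of 2% to 5%.

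**After the change.** If the main tables stop at week 16, the term (1 − a) × q × r drops out and this source of difference is zero for any a, q and r.

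**The case against.** The strongest reply is that this matters little, and much of it stands. Follow-up begins 59 days after the last planned dose and footnote i asks only for events clearly caused by the drug, so late events should be rare. Rows for events leading to drug discontinuation are hardly touched, since planned dosing ends on Day 54. The SAP plans no between-arm safety test and no dose rule based on these percentages; its primary endpoint section ties the recommended dose to the dose-response of regression. Counting every captured event over all treated women can also be defended as conservative.

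A reader might infer more than the text supports:

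- *That side-effect rows also mix all-cause and related events.* They do not. By 7.4.1 a side effect is a related event in both periods, so only unequal observation time applies to them.
- *That all-cause collection runs to week 16.* That is inferred from footnote i. Sections 4.2 and 7.4.1 end the all-cause window with the end of use, leaving the time from there to week 16 unclear.
- *That the bias always runs against the arm with more regression.* Staying in follow-up tracks the absence of CIN3 or cancer, not response. Unchanged CIN2 and CIN3 improving to CIN2 are both stable disease, yet those women stay.
- *That the imbalance is certain.* On the Section 3.1 sentence keeping all lesions of CIN3 or lower, it almost disappears.
- *That every table divides by the whole safety set.* Only 7.4.1.1 and 7.4.1.2 say so.

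What remains is a pooling rule that the SAP avoids elsewhere. Section 7.2.2 excludes concomitant drugs started after Day 112, and 7.4.2.1 tabulates laboratory values by period with week 24 separate.

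**Conclusion.** The point holds as a modest one. The text leaves the tabulated events without an end day, applies two collection rules within the adverse event rows, and lets observation time depend on the week-16 diagnosis. An arm with fewer women at CIN3 or cancer may therefore show slightly more events at equal true risk.

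Under 45% v 75% retention, 10% risk by week 16 and a late risk of 2% to 5%, the gap stays below one woman per arm. All three quantities are assumptions, and the SAP gives no rates to settle them. The size also depends on which follow-up entry wording applies. The documents do not support a claim that the safety comparison is materially biased against effective doses. The case for change is that the rows become interpretable and the outcome-dependent part is removed at very low cost.

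**What to change.** In 6.7.1 and 7.4.1:

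1. Tabulate events with onset from first dose to the week-16 visit over the safety analysis set, in all tables 7.4.1.1 to 7.4.1.6. State a fallback day for women without that visit.
2. Tabulate later events separately, labelled as related events only, with the women who entered follow-up as denominator.
3. Show serious late related events beside the main table so that none is lost from view.

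Also reconcile four wordings:

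- the event window: end of use (4.2, 7.4.1) against follow-up from week 17 (Table 1, footnote i);
- the causality threshold in follow-up: not rejected (4.2, 7.4.1) against clearly caused (footnote i);
- the denominator: observed cases (6.7.1) against target population (7.4.1.1, 7.4.1.2), stated also for 7.4.1.3 to 7.4.1.6;
- entry to follow-up: Section 1.2 against the two sentences in Section 3.1. Which rule applies is for the sponsor to say.

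The cost is SAP wording and one extra table. The small downside is that late events are read from a second table.
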